7.2.2 Handling of missing weight

In the secondary efficacy data, the body weight used to calculate prandial, basal and total daily insulin dose per unit body weight (U/kg). If the body weight value is missing, the body weight in previous visit will be used. It means the body weight will do LOCF.

7.2.3 Handling of missing or incomplete dates

Imputation rules for missing or partial AE start dates are defined below:

If only Day of AE start date is missing:

If the AE start year and month are the same as that for the first dose date, then:

- If the full (or partial) AE end date is NOT before the first dose date or AE end date is missing, then impute the AE start day as the day of first dose date;
- Otherwise, impute the AE start day as 1.

If Day and Month of AE start date are missing:

If AE start year = first dose year, then:

- If the full (or partial) AE end date is NOT before the first dose date or AE end date is missing, then impute the AE start Month and Day as the Month and Day of first dose date
- Otherwise, impute the AE start MONTH as January and the DAY as 1.

If Year of AE start date is missing:

If the year of AE start is missing or AE start date is completely missing, then query site and leave as missing.

For missing and partial adverse event end dates, imputation will be performed as follows:

If only the day of the month is missing, the last day of the month will be used to replace the missing day. If the day and month are missing or a date is completely missing, it will be considered as missing.

For the purpose of the derivation of adverse event duration, the following rules will be applied for missing/invalid onset/resolution time:

If onset time is collected and missing/invalid, onset time will be temporarily set to 00:00:01

If resolution time is collected and missing/invalid, resolution time will be temporarily set to 23:59:59

Imputation rules for missing or partial AE stop dates and the “continuing” variable indicated as “no” are defined below:

- Year is missing – date left missing.
- Month is missing – impute December.
- Day is missing – impute last date of that month.

If imputed AE stop date is before AE start date, AE stop date will be set to AE start date.

Imputation rules for missing or partial medication start dates are defined below:

If only Day of CM start date is missing:

If the CM start year and month are the same as that for the first dose date, then:

- If the full (or partial) CM end date is NOT before the first dose date or CM end date is missing, then impute the CM start day as the day of first dose date;
- Otherwise, impute the CM start day as 1.

If Day and Month of CM start date are missing:

If CM start year = first dose year, then:

- If the full (or partial) CM end date is NOT before the first dose date or CM end date is missing, then impute the CM start Month and Day as the Month and Day of first dose date
- Otherwise, impute the CM start MONTH as January and the DAY as 1.

If Year of CM start date is missing:

If the year of CM start is missing or CM start date is completely missing, then query site and leave as missing.

If the stop date for CM is missing or partially missing and the “ongoing” variable is indicated as “no”, the imputation rule is applied in the following order:

- Year is missing – Date is left missing.
- Month is missing – impute December.
- Day is missing – impute last date of that month.

7.3 Handling of site with GCP violation

During routine monitoring of this study, it was observed that one site (Site ID: 6103) had GCP compliance issues, which raised doubts on the study conduct. The blinded ADA results from the site also confirmed the need to exclude the site from results reporting. Mylan decided to conduct statistical analyses to exclude this site from ITT, Safety, and PP analysis sets. Additional sensitivity analysis to include this site (Randomized analysis set) for major baseline findings, efficacy and safety analysis will be performed. The purpose of the sensitivity analysis is to determine if major efficacy and safety analyses remain consistent with inclusion data from this site.

8 STATISTICAL METHODS

8.1 General statistical conventions

All statistical procedures will be completed using SAS version 9.3 or higher.

Unless otherwise stated, all statistical testing will be two-sided and will be performed using a significance (alpha) level of 0.05. Two-sided 95 % confidence intervals (CI) will be provided when relevant. 4 digits after decimal point will be used for all p-values.

All quantitative endpoints will be summarized using an 8-number summary (n, mean, standard deviation, median, 25th quartile, 75th quartile, minimum and maximum values). Unless otherwise specified, minimum and maximum will be presented with same number of decimal places as reported/collected, one additional decimal place for mean, median, 25th quartile and 75th quartile, and two additional decimal places for standard deviation. All qualitative endpoints will be summarized by the number of subjects meeting the endpoint and the percentage of subjects out of the appropriate population. The denominator will be displayed when needed.

For retests, unscheduled visits and visit end of treatment, in general, for by-visit summaries, data recorded at the nominal visit will be presented. Unscheduled measurements will not be included in by-visit summaries but will contribute to the scheduled visit if scheduled visit value is missing or the Last Observation Carried Forward (LOCF) value in case primary sensitivity analysis. The same principle will be applied to the visit end of treatment data.

Early termination data will be entered under the Visit 14 (week 18), but for summary tables it will be mapped to the next available planned visit number after their last scheduled visit. For example, should a patient discontinue at Visit 9, the Early Termination visit will have their Fasting plasma glucose and their HbA1c assay taken. The fasting plasma glucose would then be summarized under Visit 10 and the HbA1c under Visit 11.

All subject data, including those derived, will be presented in individual subject data listings. Unless otherwise stated, unscheduled visit results will be included in date/time chronological order, within subject listings only. All listings will be sorted by investigational site, patient number, date/time and visit. The treatment group as well as patient's sex and age will be stated on each listing. Unless otherwise stated, data listings will be based on all subjects randomized.

The visit schedules and window are shown below. If multiple records in the same visit, please use the latest one for analysis.

Study Periods	Screening	Run-in Period				Treatment Period	
Visit	V1	V2	V3	V4	V5	V6	V7
Study Week	-7 to -4	-4	-3	-2	-1	0	1
Study Day	-49 to -28	-28+/-3	-21+/-3	-14+/-3	-7+/-3	0+/-3	7+/-3
Study Day Range	[-49, -28]	[-27, -25]	[-24, -18]	[-17, -11]	[-10, -4]	[-3, 3]	[4,10]

Study Periods	Treatment Period (continue to upward table)								Follow-up
	V8	V9	V10	V11	V12	V13	V14	V15	
Study Week	2	4	8	12	16	20	22	24	28
Study Day	14+/-3	28+/-3	56+/-7	84+/-7	112+/-7	140+/-7	154+/-7	168+/-7	196+/-7
Study Day Range	[11, 20]	[21, 40]	[41, 70]	[71, 98]	[99, 126]	[127, 147]	[148, 161]	[162, 182]	[183, 203]

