4.2 Secondary efficacy endpoint(s)

The secondary endpoint points are change from baseline to week 24 for the ITT population.

- Change in HbA1c from baseline
- Change in fasting plasma glucose from baseline
- Change in prandial, basal and total daily insulin dose per unit body weight (U/kg) from baseline
- Change in 7-point SMBG profile from baseline

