8.7.3 Secondary endpoints

The following efficacy measures (both actual and change values) will be summarized at baseline and each scheduled visit.

- Change in HbA1c from baseline.
- Change in fasting plasma glucose from baseline.
- Change in prandial, basal insulin and total daily insulin dose per unit body weight (U/kg) from baseline.
- Change in 7-point self-monitored blood glucose (SMBG) profile from baseline.

A mixed model for repeated measures (MMRM) will be performed for continuous variables without imputing missing values. The MMRM model will include the fixed, categorical

effects of treatment group assignment, visit, treatment group-by-visit interaction, basal insulin dose time (AM/PM), and investigative site, as well as the baseline value as a continuous covariate.

The MMRM model results will be presented along with Least Squares (LS) means for the difference between the MYL1601-D and NovoLog[®] groups, standard errors, and two-sided 95% CIs for the difference between treatment groups. Contrasts of LS means at each scheduled visit will be used to evaluate all pairwise treatment comparisons, and 95% confidence intervals for treatment differences in LS means will be computed for each visit. The interaction of time points and treatment groups will also be presented. An unstructured covariance matrix will be assumed for within-subject error. The denominator degrees of freedom will be calculated according to the Kenward-Roger method.

In case of non-convergence of the above model using an unstructured covariance matrix, the following variance structures will be tested, and based on Akaike's information criteria the best fitting model will be chosen. The variance structures that will be considered for the within-subject variation in case of non-convergence are in this order: Heterogeneous Toeplitz, Toeplitz, and Compound Symmetry.

If convergence is still not obtained, the model may be revised to remove investigative site from the list of covariates.

All of the above analyses will be performed on the ITT set.

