8.7.3.1 HbA1c

HbA1c is collected at week -7 to -4 (visit 1), baseline, week 12 (visit 11), and week 24 (visit 15). The measurements are performed by the central laboratory.

Actual values and changes from baseline at each time point will be computed and summarized by treatment group. Treatment difference and 95% confidence interval will be displayed along with p-values.

A sensitivity analysis for HbA1c will be performed using multiple imputation to impute missing values with non-missing subjects within the same treatment group using a pattern mixture model with the complete-case missing values (CCMV) method (Little 1993). After imputation, treatment difference, 95% CI, and p-values will be generated using same MMRM model as above. Sample imputation code is provided in Appendix 10.1.4.

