proc mi data=outdata1 seed=24637883 nimpute=30  
out=outdata2;  
by treatment;  
monotone reg(hb11 hb15 / details);  
mnar model (hb11 hb15 / modelobs=ccmv(k=1));  
var hb0 hb11 hb15;  
run;
```

Step 4.

Reverse the process from Step 1, creating one record per subject visit, retaining the imputation number on each record.

Step 5.

Use code similar to what was used to analyze the primary efficacy endpoint, but run the code by `_imputation_`. For example,

```
/** step 5: Analyze the imputed datasets */  
proc sort data=imputed;  
by _imputation_ subjid avisitn;  
run;  
  
proc mixed data=imputed;  
by _imputation_;
```

```
class trt avisitn dosetime site;
model chg = trt avisitn dosetime site trt*avisitn base /
ddfm=kr s;
repeated avisitn / type=un;
lsmeans trt*avisitn / diff cl;
ods output ConvergenceStatus=converge;
ods output diffs=trtdiff;
run;
```

Convergence status is assessed by the condition that:

```
if pdg=1 and pdh=1 and status=0
```

in the dataset converge above, then model has converged. In the above code, if the model does not converge, replace the type=un option by each of the following: type=toeph, type=toep, and type=cs. You will also need to replace ddfm=kr with ddfm=bw. Choose the best fit model by checking the AIC and selecting the model with the lowest one. Please contact the statistician if this step is necessary.

Step 6.

Combine the 30 estimated statistics into one using PROC MIANALYZE.

```
data trtdiff;
set trtdiff (where=(avisitn=_avisitn));
run;

proc sort data=trtdiff;
by avisitn _imputation_;
run;

[figure not shown]
proc mianalyze data=trtdiff;
by avisitn;
modeleffects estimate ;
stderr stderr;
ods output parameterestimates=parms;
run;

proc print data=parms;
var avisitn estimate stderr lclmean uclmean probt;
run;
```

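### The SAP's early-termination rule reports HbA1c under a later visit whatever the study day, and it is not reconciled with the day windows in the same section

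*SAP*

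**What the plan says.** SAP Section 8.1 contains two rules that assign a record to a visit.

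- **Mapping rule.** Early-termination data are entered under a label of Visit 14, week 18, but "for summary tables it will be mapped to the next available planned visit number after their last scheduled visit". No limit on elapsed time is given. In the worked example a subject discontinues at Visit 9: "The fasting plasma glucose would then be summarized under Visit 10 and the HbA1c under Visit 11".
- **Window rule.** The section then gives study-day ranges for every visit: "The visit schedules and window are shown below. If multiple records in the same visit, please use the latest one for analysis". The ranges include Visit 9, Days 21–40; Visit 11, Days 71–98; and Visit 15, Days 162–182.

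HbA1c is scheduled after baseline only at Visit 11 (Week 12) and Visit 15 (Week 24), per SAP Section 8.7.3.1. SAP Section 4.2 defines the secondary endpoints as change to Week 24. SAP Section 8.7.3 states: "A mixed model for repeated measures (MMRM) will be performed for continuous variables without imputing missing values". The only HbA1c model code, in Appendix 10.1.4, indexes visits by one variable ("repeated avisitn / type=un"), and its derivation is not given.

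**The concern.** The same blood sample gets two different visits depending on which half of Section 8.1 the programmer follows, and no sentence ranks the rules. Under the mapping rule, a table headed Week 12 or Week 24 can contain HbA1c values taken weeks before that visit's window opens.

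HbA1c is secondary, but both documents name it as part of the totality of evidence that accompanies the primary TEAR comparison. What is at stake is whether Week 12 and Week 24 HbA1c results describe those weeks, and whether the tables, the mixed model and the imputation analysis rest on the same records.

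The leavers need not be a random subset. Protocol Section 5.7 lists early termination among the options at Week 16 for a subject whose HbA1c has worsened by more than 1.0% at Week 12. An HbA1c taken at that point would be reported as Week 24.

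**Working it through.** **Inputs**

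- Target days and windows: SAP Section 8.1, visit table.
- Post-baseline HbA1c visits: V11 and V15 (SAP Section 8.7.3.1). FPG visits: V9 to V13 and V15 (SAP Section 8.7.3.2).
- Timing of the early-termination visit: immediate for a subject who leaves the study (Protocol Section 4.2.3), so the sample is dated close to departure.

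**Step 1: reproduce the SAP's example.** After V9, the next planned FPG is V10 and the next planned HbA1c is V11. This matches the SAP.

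**Step 2: compare with the windows.** Gap = first day of the assigned window minus the sample day. For HbA1c in the example: 71 − 28 = 43 days. Across the V9 window, the gap runs from 71 − 40 = 31 to 71 − 21 = 50 days. Against the V11 target it is 84 − 28 = 56 days. For FPG the gap is 41 − 28 = 13 days.

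**Step 3: HbA1c for each possible last visit, sample taken at that visit's target day.**

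| Last visit (day) | Mapped to | Window opens | Days early |
|---|---|---|---|
| V6 (0) | V11 | 71 | 71 |
| V7 (7) | V11 | 71 | 64 |
| V8 (14) | V11 | 71 | 57 |
| V9 (28) | V11 | 71 | 43 |
| V10 (56) | V11 | 71 | 15 |
| V11 (84) | V15 | 162 | 78 |
| V12 (112) | V15 | 162 | 50 |
| V13 (140) | V15 | 162 | 22 |
| V14 (154) | V15 | 162 | 8 |

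The range is 8 to 78 days; 78 / 7 is about 11 weeks. A sample on Day 100 from a subject whose last visit was V11 goes to Week 24, 162 − 100 = 62 days early. The windows from V6 to V15 are contiguous and increasing, so a sample dated inside the last attended visit's window always falls before the assigned one. The rules agree only if the sample happens to be dated inside the assigned window.

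**Step 4: follow both readings into the model.**

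- If the mapped visit feeds the visit variable, early values count as observed at Week 12 or Week 24. In the complete-case (CCMV) imputation dataset of Appendix 10.1.4 they fill the Visit 11 or Visit 15 slot. A subject who attended Week 12 and left soon after could then look like a complete case.
- If the windowed visit feeds it, the Week 12 and Week 24 tables include subjects whom the model does not have at that visit, without explanation.

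**Step 5: illustrative size (assumptions, not in the documents).** Shift in one arm's raw mean = share of the arm with a mapped value × average error of that value. With shares of 2% to 10% and errors of 0.2 to 1.0 HbA1c points, the shift runs from 0.02 × 0.2 = 0.004 to 0.10 × 1.0 = 0.10 points. The treatment difference moves only by the difference between the two arms' shifts, which is zero if they are equal.

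**Step 6: the label.** In both schedules Visit 14 is the Week 22 telephone contact. The protocol treats Visit 15 as the early-termination visit (Table 1 footnote 9; Section 6.3.4). Neither schedule has a visit at Week 18.

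**The case against.** The strongest reply is that the SAP confines the mapping to summary tables and attaches the windows to analysis. A careful programmer could use the mapping for descriptive tables and the windows for the model. A reader might infer that early HbA1c values certainly enter the mixed model; the text does not say so, because the visit variable is undefined. That reply stands, but it leaves the tables reporting a roughly Day 28 value as Week 12.

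A specific rule with a worked example can also be a deliberate exception to general windows. This is fair: the two rules are unreconciled rather than flatly contradictory. An intended exception would still need stating.

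Exposure is limited. Subjects who stop treatment are asked to keep attending, and a later on-schedule HbA1c would displace the early value under the latest-record rule. Section 8.1 also says end-of-treatment data follow the rule for unscheduled data, which fill a scheduled visit only when its own value is missing. The problem therefore mainly concerns subjects who leave the study.

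Finally, dropping off-window values is not free. A subject leaving at Visit 9 would have no post-baseline HbA1c in the model, and a possibly informative value would be set aside in favour of a missing-at-random assumption. This stands and is allowed for in the fix.

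**Conclusion.** The point holds as a defect in a stated rule. The mapping has no time limit, it places HbA1c 8 to 78 days before the assigned window at target days (43 in the SAP's own example), no precedence over the windows is given, and the visit label matches no scheduled visit. Entry of these values into the mixed model and the imputation dataset is possible but not established.

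Two further inferences are tempting and unsupported. One is that the mapping pulls the comparison toward no difference. If the products truly behave alike, diluting one arm more than the other would create a difference; the direction depends on true effects and on dropout by arm, and the documents give neither. The other is a definite size of bias. Protocol Section 7.1 sets no attrition rate, and the 0.004 to 0.10 points above is an assumed shift in one arm's mean, not in the treatment difference.

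Importance is low: HbA1c is secondary, no equivalence margin is attached to it, and nothing here bears on the primary TEAR analysis. The correction is nonetheless specific and cheap.

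**What to change.** Amend SAP Section 8.1 as follows.

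1. Assign early-termination HbA1c and FPG by actual study day, using the existing windows, for tables, mixed models and imputation datasets alike. State that this is how the visit variable in Appendix 10.1.4 is derived.
2. Keep HbA1c values outside the Week 12 and Week 24 windows in listings only.
3. Say which record counts when an early-termination sample shares a window with a scheduled one, since Section 8.1 has both a latest-record rule and a rule that end-of-treatment data only fill gaps.
4. If wanted, keep the next-visit mapping as a labelled HbA1c sensitivity analysis.
5. Correct the Visit 14, week 18 label to agree with the protocol's Visit 15.

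The cost is SAP wording and a programming specification; no new data are needed. The downside is small: a few early leavers contribute no post-baseline HbA1c, and the model relies on missing-at-random for them. The optional analysis in item 4 would show whether that matters.

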6.3.5 Early Termination

Subjects can decide to discontinue entirely from the study at any time for any reason, this is documented as withdrawal of consent. Subjects can decide to discontinue from the study treatment at any time for any reason, but may choose to remain in the study for off-treatment study visits. Subjects can also be discontinued from the study or discontinued from the study treatment due to Investigator or Sponsor decision as detailed below.

The Sponsor or their representative must be notified by the Investigator as soon as possible, and prior to the early termination visit, on the decision to discontinue the subject from the study or from study treatment and provide detailed information on the reason/event.

In case of discontinuation of the subject from the study, a study termination visit (outlined as an End of Treatment visit in the Schedule of Activities) is required immediately and the site must complete the End of Study eCRF data. In case of the discontinuation of the subject from the study treatment, the subject is required to complete the End of Treatment visit, switch to marketed treatment (both basal and bolus treatments) and agree to proceed with the scheduled visits/activities.

The reason for discontinuation should be established based on the criteria for discontinuation/early termination as stated in [Section 4.2.3](#).

Subjects who decide to discontinue from treatment and agree to remain in the study, on marketed treatment, are required to adhere to the study protocol, thus perform all activities and procedures such as SMBG measurements, completing diary entries, participating in their regularly scheduled study visits for completion of all assessments and procedures as outlined in the Schedule of Activities until the Week 28 (Follow-up visit).

If the subject withdraws from the study and also withdraws consent for disclosure of future information, no further evaluations should be performed and no additional data should be collected. The Sponsor may retain and continue to use any data collected before such withdrawal of consent.

The site should explain the subject the importance of data collection and make every effort to consent the subject to continue follow up per the SCHEDULE OF ACTIVITIES until Week 28 (Follow-up visit).

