4 STUDY ENDPOINTS

4.1 Primary efficacy endpoint(s)

The TEAR rate during 24-week treatment period is the primary endpoint for this study.

TEAR is defined as either one of the following:

- 1) Subjects who are ADA negative at baseline and become positive at any timepoint post baseline
- 2) Subjects who are ADA positive at baseline and demonstrate 4-fold increase in titer values at any timepoint post baseline visit.

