 3. Run a pattern mixture model logistic regression to impute missing values to generate 30 imputed datasets. This will generate a single pooled dataset containing one observation per subject per imputation. All missing values will have been filled in for each subject.

Step 1.

The dataset for this imputation has to put the values for all weeks onto one record. That is, the dataset would have one record per subject, with 8 values for RESP0 and RESP8–RESP15. One way this can be accomplished is the following:

```
data analysis (keep=usubjid RESP0 RESP8-RESP14);
set indata;
by usubjid avisitn;
array R {9} RESP0 RESP8-RESP15;
retain RESP0 RESP8-RESP15;
if first.usubjid then do;
    resp0 = base;
    do visit = 8 to 15;
        R{visit} = .;
    end;
end;
do visit = 8 to 15;
    if avisit = visit then R{visit} = aval;
end;
if last.usubjid then output;
run;
```

STEP 2.

First a flag needs to be created to indicate which missing values need to be filled in. This is a visit-level variable for each subject. For explanatory purposes, this variable will be referred to as EMPTY_x for Visit x. For each visit where a subject has a missing value, use the logic below:

- If there is a non-missing value for any visit AFTER Visit x, then EMPTY_x=0;
- Else if there are no non-missing values for any of the remaining visits, then EMPTY_x=1;

Then all records with EMPTY_x=1 have to have their RESP_x value filled in with a randomly generated 0 or 1. One way this can be accomplished is the following:

```
/** step 2: Make missingness monotone */  
%global mylrate novrate;
```

```
%macro getrate(visnum);
```

```
    proc sort data=indata;  
        by trtgroup;  
    run;  
    ods exclude all;  
    proc freq data=indata;  
        by trtgroup;  
        table RESP&visnum;  
    ods output onewayfreqs=pct;  
    run;  
    ods exclude none;
```

```
    data binom;  
        set pct (where=(RESP&visnum=1));  
        probresp = percent/100;  
        if trtgroup="MYL-1601D" then call  
            symput("mylrate",probresp);  
        else if trtgroup="NOVOLOG" then call  
            symput("novrate",probresp);  
    run;
```

```
%mend getrate;
```

```
%macro fillin (visit);
```

```
    %getrate(&visit);
```

```
    data indata;  
        set indata;  
        if empty&visit=1 then do;  
            if trtgroup="MYL-1601D" then  
                RESP&visit=ranbin(86537043,1,&mylrate);  
            else if trtgroup="NOVOLOG" then  

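### The latest-record rule and the one-value-per-visit TEAR code can ignore a qualifying ADA sample, in conflict with the any-timepoint TEAR definition

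*SAP*

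**What the plan says.** **Endpoint.** SAP 4.1 gives the first TEAR criterion as "Subjects who are ADA negative at baseline and become positive at any timepoint post baseline". The second is a 4-fold titer rise, also at any post-baseline time. SAP 8.7.2.1 repeats this at the derivation stage: for a baseline-negative subject, any positive result, observed or imputed, suffices. SAP 8.7.1 brings all post-discontinuation data into the primary analysis.

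**Sampling at treatment stop.** For a subject who stops study treatment, Protocol 6.3.5 says "the subject is required to complete the End of Treatment visit, switch to marketed treatment (both basal and bolus treatments", and then continue with the scheduled visits. The End of Treatment visit includes an ADA draw (Protocol 6.3.4). Footnote 9 to Protocol Table 1 uses V15 both for this visit and for the Week 24 visit.

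**Record selection.** SAP 8.1 has three relevant rules.
- The nominal-visit rule is introduced with a scope: "in general, for by-visit summaries, data recorded at the nominal visit will be presented". It continues: "Unscheduled measurements will not be included in by-visit summaries but will contribute to the scheduled visit if scheduled visit value is missing", and "The same principle will be applied to the visit end of treatment data".
- Early-termination data are entered under Visit 14 and, for summary tables, moved to the next planned visit.
- Above the table of day windows stands "If multiple records in the same visit, please use the latest one for analysis", with no stated scope other than analysis.

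**TEAR code.** SAP 10.1.1 and 10.1.2 build one record per subject with one value per visit, for example "if avisit = visit then R{visit} = aval". SAP 10.1.3 then derives TEAR from those visit values for Visits 8 to 15.

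**The concern.** A latest-record rule suits a by-visit mean, where each subject should contribute once per visit. It does not suit an endpoint that asks whether a result ever occurred, because there a discarded record can be the one that decides the outcome.

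The subjects exposed are those who stop treatment, have a stop sample and continue on marketed insulin. Their stop sample comes at the end of exposure to the assigned product, and the scheduled samples after it are off study drug. If the stop sample alone is positive or 4-fold and is the record set aside, the subject becomes TEAR negative. A scheduled positive can be lost in the same way when the stop sample is the later of two in one window. The arm difference is affected, and so is the margin, which is computed from the NovoLog TEAR rate.

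**Working it through.** **Step 1: can two samples share a slot?** The Study Day Range windows in SAP 8.1 are wide, for example days 41 to 70 for Visit 10 and 71 to 98 for Visit 11. A stop sample on day 75 and a scheduled sample on day 84 both fall in Visit 11. With the V15 label instead, the stop sample and the Week 24 sample carry the same visit. The example code sorts by subject and visit, and a second record in the same visit overwrites the first.

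**Step 2: which record survives?** Assume scheduled samples on the target days (14, 28, 56, 84, 112, 140, 168), all negative, and one stop sample as the only positive. Place it on each other day from 11 to 167: 157 days less 6 scheduled days = 151 days.

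| Reading of SAP 8.1 | Days on which the stop positive is ignored |
|---|---|
| V15 label, latest record | 151 of 151 |
| Mapped to next planned visit, either selection rule | 151 of 151 |
| Day windows, scheduled value first | 137 of 151 |
| Day windows, latest record | 70 of 151 |
| Left under Visit 14 | 0 of 151 |

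The 70 days can be counted by hand as the window days before the scheduled sample: 3 + 7 + 15 + 13 + 13 + 13 + 6 = 70. On another 67 days (6 + 12 + 14 + 14 + 14 + 7) the stop sample is the later record and displaces the scheduled one. The remaining 14 days (148 to 161) lie in the Visit 14 window, which has no scheduled draw. These are counts of calendar days under a constructed case, not probabilities of loss.

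**Step 3: reproduce the margin.** SAP 8.7.2.1 gives margin = (z_α + z_β) × √(2p(1−p)/n), and the code in SAP 10.2 uses the 0.95 and 0.90 normal quantiles. With 1.6449 + 1.2816 = 2.9265 and n = 250:
- p = 5%: 2.9265 × √(2 × 0.05 × 0.95/250) = 5.70% (Table 2: 5.7%)
- p = 20%: 10.47% (Table 2: 10.5%)
- p = 50%: 13.09% (Table 2: 13.1%)

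**Step 4: effect of misclassified subjects.** Each is worth 1/250 = 0.4 points. The number is not in the documents, so the rows below are assumptions, with all losses in one arm. The second and third columns take losses in the MYL-1601D arm, the last takes losses in the NovoLog arm.

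| Lost positives | Shift in difference | Share of margin, reference rate 20% | Margin if lost in NovoLog, reference rate 20% |
|---|---|---|---|
| 1 | 0.4 points | 3.8% | 10.47% to 10.39% |
| 2 | 0.8 points | 7.6% | 10.47% to 10.31% |
| 5 | 2.0 points | 19.1% | 10.47% to 10.06% |

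At a low reference rate the effect is larger. Two NovoLog positives lost (12 to 10 of 250, or 4.8% to 4.0%) take the margin from 5.60% to 5.13%. Two lost in the MYL-1601D arm are 0.8/5.7 = 14% of the smallest margin in Table 2.

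**The case against.** The strongest reply is that the SAP's endpoint text already gives the right answer. SAP 8.7.2.1 counts any observed positive, and SAP 7.2.1 treats a subject who already meets the criteria as not missing. SAP 10.1.3 refers the derivation to ADaM specifications that are not part of these documents. The appendix is labelled as example code and will not run as printed: a nine-element array is indexed up to 15, and RESP15 is left out of the KEEP list. All of this stands. It shows that the intention is sound, but not which record reaches the derivation. SAP 8.7.2.1 also merges its datasets by subject and visit, and no sentence says that both samples in a slot are consulted.

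A reader might infer that SAP 8.1 uses a stop sample for TEAR only when the scheduled value is missing, or moves it to the next visit for TEAR. The documents do not support that. The first rule is framed for by-visit summaries and the second for summary tables. Moreover, the stated entry point for early-termination data is Visit 14, where no scheduled ADA sample competes and the value lies within the set that defines TEAR.

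The affected group is also narrow. Under reasons 3 and 4 of Protocol 4.2.3, some subjects who stop treatment and stay need no early termination visit. For subjects who leave the study, no later sample competes with the stop sample. The schedule contains no unscheduled ADA draws, so loss of such samples is hypothetical.

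**Conclusion.** The point holds as an internal conflict. The latest-record instruction is not limited to summaries and the TEAR code reads one value per visit, while the endpoint counts a qualifying result at any post-baseline time. Followed literally, these rules can class a subject TEAR negative despite a qualifying observed result. Loss is possible under every reading tried except the one that leaves the sample under Visit 14.

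The size is probably small. A subject changes status only if two samples compete for one slot and the sole qualifying result is in the record set aside. Each such subject moves an arm's rate by 0.4 points, assuming 250 per arm. The counts of lost positives used above are illustrative.

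A reader might also infer a bias towards equivalence. That does not follow. Losses in the MYL-1601D arm lower the difference, whereas losses in the NovoLog arm raise it and, at reference rates below 50%, narrow the margin. Equal losses in both arms leave the difference unchanged but still move the margin. The documents give no basis for a direction.

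**What to change.** In SAP 8.1, 8.7.2.1 and 10.1.3, state that observed TEAR is derived first, from every post-baseline ADA record, before windowing or record selection. This includes End of Treatment samples and any unscheduled ones. A subject with one observed qualifying result is then TEAR positive in every imputation. Limit the latest-record rule to by-visit tables, visitwise TEAR and the predictors in the imputation models.

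Reconcile the visit labels as well. SAP 8.1 calls Visit 14 week 18 and enters early-termination data there, while the schedule puts Visit 14 at week 22 as a telephone contact and labels the End of Treatment visit V15.

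The cost is SAP wording and one derivation step, with no new data. The small downside is that a subject who stops and stays has one more sampling occasion than a completer, which an any-timepoint definition already accepts.
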